### **8.4. Abscopal Effect Based on Non-treated Lesions at Excision**

An abscopal effect is a phenomenon whereby the treatment of target lesions leads to improvement in both treated and non-treated lesions.

A summary of (a) histologic clearance and (b) clinical clearance for non-treated lesions will be provided to investigate a possible abscopal effect using EOT data and the full analysis population.

The histologic clearance will follow Section 8.1 of this SAP except for using the histologic diagnosis of excised non-treated lesions (NTL1, NTL2, NTL3), and the clinical clearance will follow Section 8.2 of this SAP except for using the PGA of non-treated lesions (NTL1, NTL2, NTL3). The summary will be provided by clearance (Histologic, Clinical) within lesion (NTL1, NTL2, NTL3). The summary will also be run using the per-protocol population as outlined in Section 6 of this SAP.

A separate listing will be provided for the excision of all lesions as described in Section 8.1 of this SAP, and a separate listing will be provided for the PGA of all lesions as described in Section 8.2 of this SAP.

## 8.5. Physician Global Assessment

The PGA is an assessment of improvement as described in Section 8.2 of this SAP.

A summary will be provided by scheduled visit (W1D2, W1D3, W1 Safety Assessment, W2D1, W2D2, W2D3, W2 Safety Assessment, EOT, EOS 1 Week Post-excision, EOS 2 Weeks Post-excision) within lesion (TL1, TL2, NTL1, NTL2, NTL3).

The summary will use the full analysis population, and for each lesion, the number and percentage of subjects falling into each PGA category will be provided in the summary. The summary will also be run using the per-protocol population as outlined in Section 6 of this SAP.

A separate listing will be provided for the PGA of all lesions as described in Section 8.2 of this SAP.

## 8.6. Complete Clearance of Treated Lesions at Excision

Complete clearance occurs when histologic clearance, as defined in Section 8.1 of this SAP, and clinical clearance, as defined in Section 8.2 of this SAP, are both achieved.

A summary of complete clearance will be provided using histologic clearance and clinical clearance of excised treated lesions (TL1, TL2) from the end-of-treatment (EOT) visit. The clearance categories are as follows:

- Histologic Clearance (i.e., Scar) and Clinical Clearance (i.e., 100% Improvement, No Visible Tumor)
- Histologic Clearance and Not Clinical Clearance
- Not Histologic Clearance and Clinical Clearance
- Not Histologic Clearance and Not Clinical Clearance

The summary will use the full analysis population, and for each treated lesion, the number and percentage of subjects falling into each clearance category will be provided in the summary. The summary will also be run using the per-protocol population as outlined in Section 6 of this SAP.

A separate listing will be provided for the excision of all lesions as described in Section 8.1 of this SAP, and a separate listing will be provided for the PGA of all lesions as described in Section 8.2 of this SAP.

Part 2 Cohort 4, Cohort 4 Expansion, Cohort 5, Cohort 5 Expansion, and overall (Cohorts 4 and 5 and Expansion Cohorts 4 and 5, i.e., Displayed Total) will be summarized in one display; Part 1, all Part 2 cohorts, and overall (Part 2 Total) will be summarized in another display.

### **8.7. Sensitivity Analysis**

If the estimated remaining tumor volume or its related histologic diagnosis at EOT is missing for any subject lesion where a screening biopsy was performed, a sensitivity analysis will be provided using the full analysis population.

The overall maximum non-missing estimated remaining tumor volume (worst case reported across all subjects and lesions) and its related histologic diagnosis at EOT will be determined. All missing values for estimated remaining tumor volumes and histologic diagnoses at EOT will be set to the determined values mentioned previously in this section of the SAP, and two summaries with all parts/cohorts, one from Section 8.3 and one from Section 8.6 of this SAP, will then be rerun to explore sensitivity.

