## 5.2. Inferential and Descriptive Statistics

No formal inferential statistical analyses will be performed. Descriptive statistics for continuous variables will include number of subjects, mean, standard deviation, median, minimum, and maximum. Counts and percentages will be provided for categorical/ordinal variables. Unless specified in a display footnote, denominators for percentages will only consider the number of subjects being summarized or the number of non-missing responses being summarized, as appropriate. Conversion factors that may be used are as follows: 1 C = 33.8 F; 1 in = 2.54 cm; 1 kg = 2.2 lb; 1 month = 30.4375 days; 1 year = 365.25 days. The number of decimal places shown in displays will follow as closely as possible the below convention:

Statistic	Decimal Places *
n	0
Mean	1 more than Min, Max
Standard Deviation	2 more than Min, Max
Median	1 more than Min, Max
Min, Max	Same as most common in data
Percent	1

\* May be limited to less than stated as space provides

Tables will be summarized for scheduled visits unless stated otherwise in this SAP, and listings will be provided for data collected via the electronic data capture (EDC) system and from external vendor(s). If date of assessment, collection, measurement, and the like is not available, then date of visit will be used if available, where applicable. If there are multiple readings taken per visit, the most recent reading from that visit will be used in summaries, unless there are pre-dose and post-dose readings taken at the same visit, as mentioned elsewhere in this SAP.

The analyses described in this plan are considered *a priori*, in that they have been defined prior to database lock. Any analysis added after the database lock will be considered post hoc and exploratory. Post hoc analyses will be labeled as such on the displays.

Verrica Pharmaceuticals Inc.  
Protocol: VP-315-201

Statistical Analysis Plan  
6-Sep-2024

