### **5.6. Handling Dropouts and Missing Data**

Unless described otherwise in other sections of this SAP, analyses will be carried out with the data available using no imputation for missing data.

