## **6. Analysis Populations**

**Enrolled Subjects:** Enrolled subjects are subjects who signed the informed consent form and were not screen failed. Enrolled subjects will serve as the population for certain analyses as described in this SAP.

**Safety (SAF) Population:** The Safety Population will include all subjects who received at least one injection of VP-315. The SAF Population will serve as the primary population for the analysis of safety-related data.

**Full Analysis (FA) Population:** The Full Analysis Population will include enrolled subjects who received one full dose (actual equals expected for at least one treated lesion) of VP-315 (for Part 1 and Part 2 Cohorts 4 and 5, a full dose consists of two injections) and have at least one non-missing post-baseline efficacy observation for histologic clearance of lesions at excision (see Section 8 of this SAP for details). The FA Population will serve as the primary population for the analysis of efficacy-related data.

**Per-protocol (PP) Population:** The Per-protocol Population will include FA subjects who have no major protocol deviations that may substantially affect the results of the efficacy analyses outlined in Section 8 of this SAP. The final determination on protocol violations, and thereby the composition of the PP, will be made before database lock.

The PP Population will be used as the secondary population for the efficacy analyses outlined in Section 8 of this SAP.

A non-exhaustive list of potential major protocol deviations is provided below:

- Investigational Product Deviations
  - Subject received wrong treatment
  - Deviation in IP storage
  - Error in IP dosing
- Enrollment Deviations
  - Subject is enrolled prior to determining whether eligible for study
  - Ineligible subject is enrolled
  - Enrollment occurs outside protocol window
- Study Data and/or Forms Deviations
  - Forms or data not sent from clinical site to coordinating center
  - Missing data and/or form
  - Missing images and/or operative reports
- Subject Deviations
  - Subject administration of a prohibited medication
  - Subject compliance with protocol
  - Subject met withdrawal criteria but was not withdrawn
- Visit/Procedure Schedule Deviations
  - Visit/Procedure not completed
  - Visit/Procedure not completed in window

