### 7.1.1. Subject Disposition

A summary of subject disposition will be provided using enrolled subjects. The number and percentage of subjects who were enrolled, completed the study, and are included in the Safety, Full Analysis, Per Protocol, and PK Populations will be summarized, along with the reason for exclusion from the Safety, Full Analysis, Per Protocol, and PK Populations. The number and percentage of subjects discontinuing from study, and the primary reason for discontinuation from study, will also be included in the summary.

Separate listings will be provided for the following using all subjects including screen failures:

- Informed Consent (Was Subject Reconsented (Yes, No), Date of Consent/Reconsent, Date of Advarra ICF IRB Approved Version, Protocol Version Number, Version of Consent Signed (Part 1)),
- Inclusion/Exclusion (Subject Enrolled in Study (Yes, No), Enrollment Date, Part (Part 1, Part 2), Cohort (Cohort 1, Cohort 2, Cohort 4, Cohort 4 Expansion, Cohort 5, Cohort 5 Expansion), Subject Current Screen Failure (Yes, No), Subject Previous Screen Failure (Yes, No), Previous Subject ID, category/label and text for each Inclusion Criterion Not Met and each Exclusion Criterion Met for current or previous screen failure, Screen Fail Reason for current or previous screen failure), and
- Subject Visits (Visit, Date of Visit, whether Not Done, and Reason Not Done).

Separate listings will be provided for the following using enrolled subjects:

- Analysis Populations (Yes/No for Subject Inclusion in Each Population),
- End of Treatment Surgical Excision (Date Assessment Performed, All Lesions Surgically Excised (Yes, No) with Specified Reason, if applicable, Other Assessments Performed (Yes, No) with Specified Assessments, if applicable),
- End of Study Suture Removal and Post-surgical Assessment (Visit, Sutures Removed (Yes, No), Post-surgical Assessment Performed (Yes, No), Date Assessment Performed, Clinically Significant Findings (Yes, No)),

- Follow-up Call (Date of Visit, Ongoing Adverse Event Since End of Study (Yes, No), Subject Died Since Last Visit (Yes, No), Date of Death, Cause of Death (Adverse Event, Other)), and
- Subject Disposition (Enrollment Date, Date of Last Dose of Study Treatment, Date of Discontinuation or Completion of Study, Study Treatment Discontinuation and Study Discontinuation Statuses and Reasons, Date of Last Contact, and Date and Cause of Death).

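### The worst-case check in SAP 8.7 runs only in the Full Analysis population, so a fully dosed subject with no excision histology cannot change its result

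*SAP*

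**What the plan says.** **Trigger and population.** SAP 8.7 applies when the EOT remaining tumor volume or its histologic diagnosis "is missing for any subject lesion where a screening biopsy was performed". In that event "a sensitivity analysis will be provided using the full analysis population".

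**Imputed value.** The largest reported remaining volume over all subjects and lesions is found, together with its diagnosis. "All missing values for estimated remaining tumor volumes and histologic diagnoses at EOT will be set to the determined values", and one summary each from SAP 8.3 (tumor volume) and SAP 8.6 (complete clearance) is rerun.

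**Entry to the Full Analysis (FA) population.** SAP 6 requires one full dose and that the subject "have at least one non-missing post-baseline efficacy observation for histologic clearance of lesions at excision". Protocol 11.3 defines its full analysis set with the same two exclusions.

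**Excision and its absence.** Protocol 8.3 requires every subject to return for excision, including those who stop study drug early. Protocol 7.1 nevertheless provides for subjects who do not complete all excisions: they may be replaced, except where they left because of treatment-related toxicity. Protocol 9.1 lists withdrawal of consent and loss to follow-up among the reasons for leaving the study.

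**The concern.** A worst-case imputation is meant to show how far the result could move if the unobserved outcomes were all unfavourable. Here, having some histology is a condition of entering the population in which missing histology is imputed. The check can fill in a second lesion that was not read, but it cannot respond to a subject for whom nothing was read.

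The gap is widest for subjects with a single lesion. SAP 8 says every subject has TL1 but not every subject has more. A subject with TL1 alone is in FA only if TL1 has a histology result.

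At stake is the interpretation of the clearance and tumor-volume tables. The stated secondary objective for Cohorts 4 and 5 is to confirm antitumor efficacy, and the primary objective there is to support the design of a pivotal study. A reader who sees the sensitivity table equal or close to the main table may conclude that missing histology does not matter, when the most incomplete subjects were never in either table.

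**Working it through.** **Step 1: can a fully dosed subject with no histology affect the 8.7 result?**
- Through the denominator or numerator: no. The subject fails the FA histology condition, and 8.7 is run in FA.
- Through the imputed value: no. That value is the maximum of reported volumes, and this subject reports none.

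The change is exactly zero for any number of such subjects. If they are the only missing data, the rerun reproduces the main table.

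**Step 2: what would counting them do?** The documents give no clearance rate and no count of subjects without histology, so there is no planned figure to reproduce.

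Inputs:
- N = 36 + 37 = 73, Cohorts 4 and 5 (SAP 3.6 and 3.7).
- k = number of fully dosed subjects with no excision histology. Assumed; it may be 0.
- p = TL1 histologic clearance rate in FA. Assumed.
- All N subjects are taken to meet the dose criterion, and the other N-k to have TL1 histology.

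Cleared lesions number p(N-k). With the k subjects kept as not cleared, the rate is p(N-k)/N, a fall of pk/N.

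| k (assumed) | (N-k)/N | fall at p=30% | fall at p=50% | fall at p=70% |
|---|---|---|---|---|
| 0 | 1.000 | 0 | 0 | 0 |
| 1 | 72/73 = 0.986 | 0.4 points | 0.7 | 1.0 |
| 4 | 69/73 = 0.945 | 1.6 | 2.7 | 3.8 |
| 7 | 66/73 = 0.904 | 2.9 | 4.8 | 6.7 |

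In whole subjects with k=7: 33/66 = 50.0% in FA becomes 33/73 = 45.2%. The same factor applies to complete clearance, since a lesion not cleared histologically cannot be completely cleared.

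**Step 3: single display columns.** SAP 5.5 shows initial and expansion groups separately. One such subject in a group of 10 gives 9/10 = 0.900. Two in the Cohort 4 expansion (26) give 24/26 = 0.923, and two in the Cohort 5 expansion (27) give 25/27 = 0.926.

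**Step 4: mean remaining volume.** If m is the FA mean and Vmax the imputed value, the mean rises by (Vmax-m)k/N. With assumed m=20, k=4 and N=73, the rise is 80×4/73 = 4.4 points for Vmax=100 and 40×4/73 = 2.2 points for Vmax=60.

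**The case against.** **The cases should be rare.** Protocol 8.3 requires excision of everyone, and willingness to undergo it is an inclusion criterion (protocol 5.2). This stands. No passage supports any particular k, and the larger values above are only illustrations. Rare is not excluded, however. Protocol 7.1 and 9.1 name toxicity, withdrawal and loss to follow-up, and replacement refills the evaluable count without bringing the replaced subject into FA.

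**The bound can be worked out by hand.** SAP 7.1.1 tabulates the population counts "along with the reason for exclusion from the Safety, Full Analysis, Per Protocol, and PK Populations", and the excision and PGA listings (SAP 8.1, 8.2) cover all enrolled subjects. That is largely true for the clearance rate. It still leaves these subjects out of every clearance summary.

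**The trigger may be meant for FA subjects only.** The sentence can be read that way. The result is the same, because a subject with no histology is outside the rerun on either reading. Nor is 8.7 empty: it works for an FA subject with one lesion read and another missing.

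**Stronger readings that the documents do not support.**
- *The efficacy results are biased upward.* The worst-case count can only lower the rate, by construction. The true direction is unknown, because nothing is said about the outcomes of subjects without histology.
- *Complete clearance is undefined when the EOT Physician Global Assessment (PGA) is missing.* SAP 5.6 says "analyses will be carried out with the data available using no imputation for missing data", and protocol 11.1 defaults to non-missing denominators. SAP 5.2 is looser ("denominators for percentages will only consider the number of subjects being summarized or the number of non-missing responses being summarized, as appropriate") but does not contradict this. SAP 8.6 equates clinical clearance with the top PGA category, so 'Not Applicable' can be read by complement as not cleared, for example under "Not Histologic Clearance and Not Clinical Clearance". A clarifying line would help, but this is not an error.
- *Protocol 11.5.3 (all enrolled subjects) conflicts with 11.3 and leaves the efficacy population open.* The SAP follows 11.3 and takes precedence (SAP 13).

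**Conclusion.** The point holds as a limit on one sensitivity analysis. As written, SAP 8.7 cannot respond to fully dosed subjects with no excision histology, and it is the only planned check on missing histology. That part follows from the text and needs no assumption.

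The size depends on k, which the documents do not give. If k is zero, nothing changes. For Cohorts 4 and 5 together, k=1 to 4 would lower a 50% TL1 rate by 0.7 to 2.7 points in the worst case; a single column of 10 subjects would move more. The study plans no inferential analysis and states no efficacy threshold, and its primary objectives concern safety, tolerability and dosing. No test, decision rule or primary safety conclusion is affected. This is a cheap improvement to the robustness of a descriptive secondary result.

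**What to change.** Keep FA as the primary efficacy population and keep 8.7 as it stands. Add to 8.7, in substance:

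> The 8.3 and 8.6 summaries for treated lesions (TL1, TL2) will also be rerun in all subjects who meet the FA dose criterion, regardless of histology. Every treated lesion with missing EOT histology stays in the denominator, takes the worst-case remaining volume determined in this section and counts as not histologically cleared. A missing EOT PGA counts as not clinically cleared.

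The cost is this wording and two extra reruns of existing tables, with no new data. The sensitivity figure may be less favourable than the FA figure. SAP 1 requires changes before database lock; if lock has passed, SAP 5.2 would have the rerun labelled post hoc.

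Optional clarifications, none of which corrects an error:
- a further rerun in the Safety Population, which would show the effect of the dose criterion rather than of missing histology;
- a line in 8.6 stating the denominator and the place of a 'Not Applicable' PGA;
- an entry in SAP 14 for the difference between protocol 11.3 and 11.5.3.

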## **9. Safety Analysis**

The conventions of Section 5 of this SAP will be applied. Tables and figures will be prefixed with 14, and listings will be prefixed 16. Tables will be provided for Part 1 and Part 2 unless noted otherwise.

### **9.1. Adverse Events**

Adverse event (AE) summaries will be based on treatment-emergent adverse events (TEAEs). TEAEs are defined as AEs that started or worsened upon or after study treatment initiation. If it cannot be determined whether an AE is treatment emergent due to an incomplete or missing onset date and/or time, the AE will be considered treatment emergent. All AEs will be summarized using the safety population.

For AEs that are cutaneous injection site reactions (Erythema, Induration, Swelling, Blister Formation/Vesicles, Desquamation/Exfoliation, Erosion, Ulceration, Necrosis), severity was intended to be assessed on a cutaneous reaction assessment (CRA) grading scale (None (1), Mild (2), Moderate (3), Severe (4), Not Applicable (5)) and for all other AEs, severity was intended to be assessed according to the Common Terminology Criteria for Adverse Events (CTCAE) version 5.0 grading scale (Mild (1), Moderate (2), Severe (3), Life-threatening (4), Fatal (5)).

As the actual AE grading scale used was not captured in EDC, and the meaning of the grades is different across scales, the Maximum Severity and Grade  $\geq 2$  summaries will

be split into two sets, one for AEs that are cutaneous injection site reactions and one for AEs that are not cutaneous injection site reactions. For cutaneous injection site reactions, the preferred terms (PTs) that will be used are as follows: Injection site erythema, Injection site induration, Injection site swelling, Injection site vesicles, Injection site exfoliation, Injection site erosion, Injection site ulcer, Injection site necrosis.

An overall summary of adverse events will be provided where the number of TEAEs and the number and percent of each of the following items will be displayed.

- Subjects with at least one:
  - TEAE
  - TEAE by Strongest Relationship to Study Treatment (Not Related, Related)
  - TEAE Excluding Cutaneous Injection Site Reactions by Maximum Severity (Mild, Moderate, Severe, Life-threatening, Fatal)
  - TEAE of Only Cutaneous Injection Site Reactions by Maximum Severity (Mild, Moderate, Severe)
  - Grade  $\geq 2$  Events Excluding Cutaneous Injection Site Reactions:
    - TEAE
    - TEAE by Strongest Relationship to Study Treatment
    - TEAE Occurring upon Study Treatment through Observation Period (explained in detail below)
    - TEAE with Local Reactogenicity (Injection site pain)
    - TEAE with Systemic Reactogenicity (Fever, Myalgia, Headache)
  - Severity  $\geq$  Moderate Events of Only Cutaneous Injection Site Reactions (excluding Severity = Not Applicable):
    - TEAE
    - TEAE by Strongest Relationship to Study Treatment
    - TEAE Occurring upon Study Treatment through Observation Period
    - TEAE with Local Reactogenicity (Injection site erythema, Injection site induration)
  - Serious TEAE
  - DLT - Part 1 Only
  - TRAE SI - Part 2 Only
  - TEAE Leading to Study Treatment Discontinuation

Verrica Pharmaceuticals Inc.  
Protocol: VP-315-201

Statistical Analysis Plan  
6-Sep-2024

- TEAE Leading to Study Discontinuation
- TEAE Leading to Death

Categories for Relationship to Study Treatment are Related and Not Related, and categories for Severity are Mild, Moderate, and Severe where the severe category will include severity levels of severe, life-threatening, and fatal as applicable.

Summaries of DLT events, TRAE SI events, and TEAEs for a subject Occurring upon Study Treatment through its Observation Period (e.g. during the DLT observation period or TRAE SI observation period) are TEAEs that a subject experiences on any day on which treatment occurs. This definition of the DLT and TRAE SI observation periods deviates from the protocol as described in section 14.

In addition, for each of the nineteen listed item mentioned previously in this section of the SAP, summaries for the total number of TEAEs, the number and percentage of subjects with at least one TEAE, and the number and percentage of subjects with at least one TEAE categorized by system organ class (SOC) and PT will be provided. Subjects having more than one AE may appear in more than one SOC or PT but will be counted at most once per each SOC and PT. For maximum severity, subjects will be counted at the most extreme category among the mild, moderate, and severe categories. For relationship to study treatment, subjects will be counted at the most related category among the unrelated and related categories. SOC and PT will be displayed in order of decreasing frequency of total SOC count, followed by decreasing frequency of total PT count, and then alphabetically if tied.

Local reactogenicity is defined as the following events: Injection site pain, Erythema, Induration. For local reactogenicity, the PTs that will be used are as follows: Injection Site Pain, Injection Site Erythema, Injection Site Induration. Systemic reactogenicity is defined as the following events: Fever, Myalgia, Headache. For systemic reactogenicity, the PTs that will be used are as follows: Fever, Myalgia, Headache.

A separate listing will be provided for all AEs using the safety population, and the listing will include the following:

- Subject Experience any Adverse Events (Yes, No),
- Adverse Event,
- TEAE (Yes, No),
- DLT (Part 1) or TEAE SI (Part 2) (Yes, No),
- Start Date and End Date (or Ongoing),

- Severity (Mild, Moderate, Severe, Life-threatening, Death),
- Serious (Yes, No),
- Relatedness (Related, Not Related),
- Action Taken (No Action Taken, Dose Reduced, Dose Interrupted, Drug Withdrawn, Not Applicable),
- Outcome (Resolved/Recovered, Resolved/Recovered with Sequelae, Not Resolved/Not Recovered, Resolving/Recovering, Fatal, Unknown),
- Related to Screening (Yes, No), and
- Screening Assessment if Related to Screening.

Additionally, a separate listing will be provided for all SAEs using the safety population, and the listing will include the following:

- Serious Adverse Event,
- Start Date and End Date (or Ongoing) where End Date (or Ongoing) is taken from reported AEs,
- Report Version (Initial, Follow-up, Final),
- Reason for Reporting (Resulted in Death, Life-threatening, Required Prolonged Hospitalization, Persistent or Significant Disability, Congenital Anomaly/Birth Defect, Important Medical Event),
- Death Date,
- Hospitalization Date,
- Autopsy (Yes, No),
- Death Certificate (Yes, No),
- Date Event Became Serious, and
- Date Event Became Non-serious.

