### 4.1. Treatment-related Adverse Events

TRAEs are treatment-emergent adverse events that are related to study treatment.

Adverse events (AEs) considered DLTs (Part 1) or TRAEs SI (Part 2) are defined as follows. AEs considered DLTs or TRAEs SI are captured in EDC.

- Hypotension meeting any of the following definitions:
  - > 20 mmHg decrease in systolic blood pressure (BP) with absolute systolic BP < 100 mmHg, or
  - > 20 mmHg decrease in systolic BP with clinical symptoms, or
  - absolute diastolic BP < 60 mmHg
- Significant elevation of serum tryptase concentration is defined as an increase of  $(1.2 \times \text{baseline value}) + 2$
- Any Grade 2 or higher AE occurring between start of dose administration and the end of the post-dose observation period on any given treatment day
- Any Grade 2 or higher AE considered by the investigator to be related to the investigational product
- Any Grade 2 or higher local reactogenic AE (injection site pain, erythema, induration)
- Any Grade 2 or higher systemic reactogenic AEs (fever, myalgia, headache)

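### SAP 9.3 counts a systolic fall with symptoms only if the symptom is already flagged as a DLT or TRAE SI, so the row cannot find a case the flag missed

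*SAP*

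**What the plan says.** **The criterion.** SAP 4.1, like protocol 10.2, gives three hypotension definitions, any one of which makes a related event a DLT or TRAE SI:

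- a systolic fall above 20 mmHg with systolic below 100;
- a systolic fall above "20 mmHg decrease in systolic BP with clinical symptoms, or" the third alternative;
- diastolic below 60.

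Four of the other criteria are grade-based, for example "Any Grade 2 or higher AE considered by the investigator to be related to the investigational product".

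**The grading scales.** SAP 9.1 says that cutaneous injection-site reactions were meant to be graded on a "cutaneous reaction assessment (CRA) grading scale (None (1), Mild (2), Moderate (3), Severe (4), Not Applicable (5" and all other events on CTCAE version 5.0.

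**The flag.** SAP 4.1 states: "AEs considered DLTs or TRAEs SI are captured in EDC". The AE listing in SAP 9.1 carries it as "DLT (Part 1) or TEAE SI (Part 2) (Yes, No". For the AE tables, DLTs and TRAE SIs "are TEAEs that a subject experiences on any day on which treatment occurs".

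**The tabulation.** SAP 9.3 counts events and subjects for each hypotension definition at each injection visit. The systolic fall is measured in three ways: from baseline, from the same day's pre-injection reading, and from the previous reading. For the definition with symptoms, the symptom must be a treatment-emergent event that starts on the date of the fall and meets three conditions:

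- (a) it is recorded as a DLT or TRAE SI;
- (b) it is related to treatment;
- (c) it is one of eight preferred terms: dizziness, dyspnoea, syncope, nausea, hyperhidrosis, blurred vision, headache or fatigue.

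The other two hypotension rows carry no flag condition.

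**The concern.** A table built from the readings is useful because it does not depend on what the site decided to flag. Condition (a) removes that independence for one of the three rows. It requires the symptom to be a DLT or TRAE SI in its own right, although under the criterion the symptom only has to accompany the fall.

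Hypotension is an acute effect that the protocol anticipates; section 2.3.1 gives it as one reason for splitting the dose. A reader who sees zero or a very low count in this row would take it as evidence that symptomatic falls were rare. The row cannot support that conclusion.

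**Working it through.** **1. Criterion against tabulation rule**

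| Element | SAP 4.1 / protocol 10.2 | SAP 9.3 |
|---|---|---|
| Systolic fall | yes | yes, measured three ways |
| Clinical symptom | yes, no list | one of eight terms, same date |
| Related to treatment | yes | yes, condition (b) |
| Symptom itself a DLT or TRAE SI | not required | required, condition (a) |

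The date match and the term list make the criterion programmable. Condition (a) narrows it. SAP 14 lists the departures from the protocol, and this is not among them.

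**2. Part 2: the row repeats the flag.** A counted fall occurs at an injection visit and the symptom starts that day. Condition (a) says the symptom is flagged. So every counted subject already has a flagged TRAE SI on a treatment day. The TRAE SI row in SAP 9.1 appears to rest on the same flag; this is inferred from SAP 4.1 and the AE listing, because 9.1 does not say so outright.

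**3. A site that flags correctly can still lose the case.** Suppose the site records hypotension as the TRAE SI and a related Grade 1 dizziness as a separate, unflagged event. SAP 4.1 has six criteria, and four need Grade 2 or higher. At Grade 1, 0 of the 8 symptom terms meet any of those four, so the dizziness has no grade-based reason to be flagged. The subject meets the criterion but is not counted in this row. The only term with another route is headache (1 of 8), which protocol 7.3.2.2 lists as a TRAE SI without a grade.

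**4. What the other rows recover.** One row catches a fall with systolic below 100, and another catches diastolic below 60. The cases missing from all three rows are therefore those with

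- a systolic fall above 20 mmHg,
- systolic at or above 100 and diastolic at or above 60, and
- a related, same-day listed symptom that is not itself flagged, typically Grade 1.

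**5. Part 1.** SAP 3.1 gives N = 10. SAP 3.2 and protocol 2.3.2 say there were no DLTs. If no event carries the DLT flag, condition (a) is never met and the row is 0/10 for every pressure and symptom record.

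**6. Weight of one subject.** The group sizes in SAP 3.3 to 3.7 reproduce the stated Part 2 total: 6 + 3 + 10 + 26 + 10 + 27 = 82. With the full group as denominator:

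| Group | N | One subject = 100/N points |
|---|---|---|
| Part 1 | 10 | 10.0 |
| Cohort 1 | 6 | 16.7 |
| Cohort 2 | 3 | 33.3 |
| Cohorts 4 and 5, initial | 10 each | 10.0 |
| Cohort 4 Expansion | 26 | 3.8 |
| Cohort 5 Expansion | 27 | 3.7 |
| Part 2 total | 82 | 1.2 |

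If 0 to 3 subjects were omitted (an assumption), the shift would be 0 to 11.5 points in Cohort 4 Expansion (3/26), 0 to 11.1 in Cohort 5 Expansion (3/27) and 0 to 3.7 in the total (3/82). These are weights, not estimates of bias.

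**The case against.** **On the row itself.** This is a supportive vital-signs table in a descriptive study. Falls to systolic below 100 or diastolic below 60 are counted elsewhere without the flag, a related Grade 2 symptom should be flagged in its own right, and all readings and events are listed. The flag may also help to tie a symptom to the fall. In Part 1 a related symptomatic fall in the DLT period would itself be a DLT, so zero agrees with the report of no DLTs.

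Much of this stands, and it confines the loss to the cases in step 4 of the working. It does not justify the condition. Listings are not counts. Relatedness, the date match and the term list already guard against coincidence. Agreement with the DLT report is no check when the row is computed from that report.

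**A stronger reading.** A reader might infer that the TRAE SI count, a Part 2 primary endpoint, is itself unreliable. SAP 9.1 says "As the actual AE grading scale used was not captured in EDC". Mild is 2 on the CRA codes but 1 on CTCAE, and the cutaneous rows were moved to Severity at or above "Moderate Events of Only Cutaneous Injection Site Reactions (excluding Severity = Not Applicable") with no matching rule for TRAE SI. The documents do not support that inference:

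- Protocol 7.3.2.2, 7.4.2 and 7.4.3 point to CTCAE version 5.
- Section 7.3.2.2 exempts Grade 1 local reactions. That makes sense on CTCAE but not on codes where 1 means none.
- The reaction form in protocol Appendix 1 has words and no numbers.
- The medical monitor reviews each TRAE SI.
- The component rows in SAP 9.1, and the listing with flag and severity side by side, already allow a check.

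No flagging error is shown. A derived TRAE SI count would rest on the same recorded severity, so it is optional.

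**Conclusion.** The point holds for SAP 9.3 and should be fixed. Condition (a) is not in the criterion and is undeclared in SAP 14. It makes the row circular in Part 2 and, if no Part 1 event carries the DLT flag, zero by construction there. The number of subjects affected cannot be computed from the documents and may be none.

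Two further inferences would go too far. The documents do not show that any symptomatic fall occurred and was omitted. Nor does anything make the TRAE SI row in SAP 9.1 depend on the 9.3 table, so this is not a demonstrated error in the primary endpoint. What is affected is one reported safety count for a known acute effect of the drug.

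**What to change.** In SAP 9.3, delete condition (a) for both parts. Keep relatedness, the date match, the eight preferred terms and all three definitions of systolic decrease, with the count shown under each. If the database is already locked, label the revised row post hoc, as SAP 5.2 requires.

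The cost is one condition removed from the blood-pressure program; no new data are needed. The change can only raise the count or leave it as it is. There are two limits:

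- It may admit a same-day symptom that was judged related but only coincided with the fall.
- It does not recover a case where the site recorded hypotension alone with no separate symptom event, because hypotension is not among the eight terms.
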